9.3.2. Information Collected During the Follow-Up Period

The following information will be collected (unless otherwise noted) by the Prescribing Physician at each routine clinical practice visit, and also recorded. Visits are anticipated to occur approximately every 6 months. See also the Schedule of Events (Section 16.1).

- SAEs, including but not limited to infections (including opportunistic infections), hepatic events, malignancies, and renal events (note: all opportunistic infections and malignancies are to be reported as SAEs);
- AEs (including laboratory abnormalities) leading to treatment discontinuation;
- concomitant use of immunomodulatory, immunosuppressive (including corticosteroids), and anti-neoplastic agents, and other approved MS therapies (if any)
- concomitant use of hepatotoxic and nephrotoxic agents (e.g., paracetamol, nonsteroidal anti-inflammatory drugs, antibiotics, anticonvulsants, protease inhibitors, diuretics, and lithium) (if any)
- complete blood count (CBC) with differential, *if consistent with local regulations*††
- results of other clinical laboratory test results recommended in the local label (e.g., liver and renal function tests, urinalysis) *if consistent with local regulations*††
- recording of EDSS information (including Functional System Scores and Ambulation scores), based on neurological examination, *when collected as part of routine clinical practice* (i.e., not specifically performed for the study) †††
- recording of MS relapse information (see below for the definition of relapse)
- DMF prescription and utilization information, including prescribed dosing frequency, duration of DMF use, and primary reason for discontinuation of DMF

CONFIDENTIAL

The information contained herein may not be used, disclosed, or published without the written consent of Biogen Idec MA Inc.

- patient assessment of the following outcome measures, *if consistent with local regulations*: MSIS-29, EQ-5D and EQ VAS, MFIS-5, WPAI-MS, and healthcare resource consumption (as described above)††††
- pregnancy status (patient-reported, female patients) †††††

††**Note**: At sites in the US, physicians will be asked to conduct blood draws for CBC (not more frequently than every 12 months unless indicated per local standard of care) and to record the results. To be consistent with local regulations, physicians in the EU and ROW will be asked to record CBC, liver function, renal function, and urinalysis results *if collected as part of routine clinical practice* (i.e., not specifically performed for the study). Additionally, if a patient discontinues DMF due to an abnormal laboratory test result, physicians will be asked to record all relevant laboratory test results collected during the study (starting with the most recent values prior to initiating DMF) *as part of routine clinical practice*.

[figure not shown]
†††**Note**: In order to assure high reliability of assessments, it is essential to have standardized examinations and consistent definitions for the EDSS. Neurostatus certification is highly recommended for all participating physicians. Physicians will be asked to provide their certification information. If they are not certified, they will be provided a copy of the interactive Neurostatus Training DVD-ROM edited by L Kappos and S Wu, Basel – Switzerland and offered a free-of-charge online certification training (www.neurostatus.net).

††††**Note**: PROs will be available to patients online or on paper to allow completion of the questionnaires outside of the physician's office. However, the questionnaires are to be completed within 1 week (before or after) the scheduled visit. Questionnaires may be completed by a proxy (e.g., family member).

†††††**Note**: Pregnancy status will not be collected for female patients who are enrolled in the study but have not initiated treatment with DMF.

Definition of Relapse

For the purposes of this study, relapses are defined as new or recurrent neurologic symptoms not associated with fever, lasting at least 24 hours. New or recurrent neurologic symptoms that evolve gradually over months are to be considered disease progression, not an acute relapse. New or recurrent neurologic symptoms that occur fewer than 30 days following the onset of a relapse as defined above are to be considered part of the same relapse.

CONFIDENTIAL

The information contained herein may not be used, disclosed, or published without the written consent of Biogen Idec MA Inc.

9.4. Data Sources

In the prospective cohort study, individual patient data will be collected at routine clinic visits (see Sections 9.2.1.2 and 9.3).

Background comparator rates for AEs of interest and any new potential safety signals identified will be ascertained using external databases (see Section 9.2.2).

9.5. Study Size

A sample size of approximately 5000 MS patients who have been newly prescribed DMF will be enrolled in the study and followed for up to 5 years. Follow-up is planned regardless of whether patients do not initiate or discontinue treatment with DMF. Enrollment will close after 5000 enrolled MS patients have been treated with DMF (defined as having taken at least 1 dose of DMF). The sample size and study duration were chosen to ensure a reasonable likelihood of observing rare events over a 5-year period and calculating informative confidence intervals (CIs) for SAE incidence and incidence rate point estimates.

Based on withdrawal rates observed in DMF clinical trials and prior Biogen Idec observational studies, it is expected that approximately 16,000 to 18,000 person-years of follow-up will accrue. Enrollment may be increased if the withdrawal rate is substantially greater than expected.

With this sample size, the probability of observing an event with an incidence of 0.06% (60/100,000 persons, or 1/1667 persons) will be 95%, the probability of observing an event with an incidence of 0.05% (50/100,000 persons, or 1/2000 persons) will be 92%, and the probability of observing an event with an incidence of 0.03% (32/100,000 persons, or 1/3125 persons) will be 80%.

In addition, the study's estimated power to detect potential clinically relevant increases in the risk of malignancies, serious infections, serious hepatic events, and serious renal events in a given year, as compared to expected background rates, is shown in Table 4. These power calculations assume a sample size of 5000 patients and an exact binomial test with a nominal, 2-sided significance level of 0.05.

CONFIDENTIAL

The information contained herein may not be used, disclosed, or published without the written consent of Biogen Idec MA Inc.

Table 4: Estimate of Power for Detecting Potential Clinically Relevant Increases in the Risk of Events of Interest Compared With Expected Background Rates

Outcome	Expected	Risk Ratio	Power (%)
Malignancies ^{1, 2}	449.9/100,000 persons/year	2.0	97
Serious infections ³	2000/100,000 persons	1.5	99
Serious hepatic events ^{3, 4}	130/100,000 persons	2.5	82
Serious renal events ³	260/100,000 persons	2.0	86

¹ Source data: SEER; Fast Stats: an interactive tool for access to SEER cancer statistics. Surveillance Research Program, National Cancer Institute. <http://seer.cancer.gov/faststats>. Accessed on 20 January 2012.

² Excludes basal and squamous cell carcinomas of the skin, except when these occur on the skin of the genital organs, and in situ cancers, except urinary bladder.

³ Source data: incidence in placebo arms of Studies 109MS301 and 109MS302

⁴ No placebo subjects in Studies 109MS301 and 109MS302 experienced a serious hepatic event; for the purpose of power calculations, 1 placebo subject was imputed.

Table 5 shows the SAE incidence and incidence rate point estimates and 95% CIs for various scenarios of observed number of cases. The SAE incidence was calculated based on the assumption of 5000 patients in the analysis population. The SAE incidence rate was calculated based on the assumption of observing 17,000 person-years of follow-up. The 95% CIs were calculated based on the binomial distribution for SAE incidence and based on the Poisson distribution for SAE incidence rates.

Table 5: SAE Incidence and Incidence Rate: Point Estimates and 95% Confidence Intervals Based on Number of Observed Cases

Number of Observed Cases (in 5000 patients with 17,000 person-years of follow-up)	SAE Incidence		SAE Incidence Rate (per 100,000 person-years)	
	Point Estimate	2-sided 95% CI	Point Estimate	2-sided 95% CI
1	0.02%	(0.001%, 0.111%)	5.9	(1.5, 32.8)
2	0.04%	(0.005%, 0.144%)	11.8	(3.6, 42.5)
3	0.06%	(0.012%, 0.175%)	17.7	(6.4, 51.6)
4	0.08%	(0.022%, 0.205%)	23.5	(4.5, 60.2)
5	0.1%	(0.032%, 0.233%)	29.4	(9.6, 68.6)
10	0.2%	(0.096%, 0.367%)	58.8	(28.2, 108.2)
20	0.4%	(0.244%, 0.617%)	117.6	(71.9, 181.7)

CONFIDENTIAL

The information contained herein may not be used, disclosed, or published without the written consent of Biogen Idec MA Inc.

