9.2.1.2. Overall Study Duration and Follow-Up

The study consists of enrollment and a follow-up period. Patient participation in the study will be for up to 5 years from enrollment. Follow-up is planned regardless of whether patients who have been prescribed DMF do not initiate treatment or discontinue treatment with DMF.

CONFIDENTIAL

The information contained herein may not be used, disclosed, or published without the written consent of Biogen Idec MA Inc.

Enrollment

The decision to enroll a patient in this study must not be made until after the Prescribing Physician and patient decide to begin DMF treatment and DMF has been prescribed. Patients agreeing to participate in the study will read and sign the consent and confidentiality statements. Enrollment data will be collected by the physician at the routine clinical visit at which DMF treatment is first prescribed (see Section 9.3.1 for details). During enrollment, the physician will also inform female patients of childbearing potential about the DMF Pregnancy Registry (in countries where the registry is conducted).

Patients enrolled in the study will be assigned unique patient ID numbers that will be used to track the patients throughout the study. Any patient identification numbers that are assigned will not be reused even if a patient does not start DMF treatment.

[figure not shown]
An individual study patient may only be included once in the study. Patients who prematurely withdraw from the study for any reason will not be eligible to re-enroll.

Follow-Up

After enrollment, the Prescribing Physician will collect patient information during routine clinical visits as described in Section 9.3.2. For the purposes of this study, routine clinical visits are defined as any visit scheduled per local standard of care. The collected information for each patient will be sent to the Contract Research Organization (CRO) managing the study (see Section 3) through their Coordinating Center (CC) approximately every 6 months for up to 5 years after enrollment. If the CC does not receive completed data from the physician on a patient for whom 6-month follow-up is expected, the CC will contact the site to remind them to complete the required data.

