9.2.1.3. Discontinuation or Withdrawal of Patients from the Study

9.2.1.3.1. Discontinuation of DMF and Continued Participation in the Study

Patients who discontinue treatment with DMF will have the option to continue participating in the study. The Prescribing Physician will record the primary reason for

CONFIDENTIAL

The information contained herein may not be used, disclosed, or published without the written consent of
Biogen Idec MA Inc.

DMF discontinuation, including AEs (including laboratory abnormalities) leading to discontinuation. If the primary reason for discontinuation of DMF was a laboratory finding, the patient's complete history of relevant laboratory values collected during the study (starting with the most recent values prior to initiating DMF [see Section 9.3.1]) is also to be recorded. Information will be collected at routine clinical visits following the standard protocol as described in Section 9.3.2 through 30 days after the last dose. At routine visits thereafter, the standard protocol will also be followed, except SAE data collected will be limited to reports of malignancies. In the event that a patient does not have a routine visit within 6 months after his/her last dose of DMF, the physician will contact the patient by telephone to obtain the information, with the exception of laboratory data and EDSS score.

It should be noted that patients who discontinue treatment with DMF but continue to be followed in the study should have the option of restarting DMF treatment at any time within the 5-year follow-up period. Once a patient has restarted DMF, the information collected should follow the standard protocol.

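### Section 9.5 sizes SAE-rate precision and its enrolment clause on study follow-up and withdrawal, although for SAEs other than malignancies the observable time also depends on how long patients stay on DMF

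*Protocol*

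**What the plan says.** Protocol Section 9.5 (Study Size) says that "it is expected that approximately 16,000 to 18,000 person-years of follow-up will accrue". Its only stated reason for enlarging the study is that "Enrollment may be increased if the withdrawal rate is substantially greater than expected". The withdrawal rate is neither defined nor given a number. Enrolment otherwise has a fixed end: "Enrollment will close after 5000 enrolled MS patients have been treated with DMF".

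The follow-up counted here continues off drug: "Follow-up is planned regardless of whether patients do not initiate or discontinue treatment with DMF". Table 5 applies the same quantity to SAE rates in general: "The SAE incidence rate was calculated based on the assumption of observing 17,000 person-years of follow-up".

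Section 9.2.1.3 separates two events. Under 9.2.1.3.1, "Patients who discontinue treatment with DMF will have the option to continue participating in the study". Section 9.2.1.3.3 deals with leaving the study by withdrawing consent. For patients who stop DMF and stay, the standard data collection runs to 30 days after the last dose, and then: "At routine visits thereafter, the standard protocol will also be followed, except SAE data collected will be limited to reports of malignancies". Sections 11.2.2 and 11.2.4 and Table 7 (chart 2, footnote 4) repeat the 30-day limit. The comment under Section 5 of the ENCePP checklist in Annex 2 gives 6 months instead. These places must be reconciled.

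The primary endpoint (Section 9.1.1) includes SAE incidence rates. Section 9.7.3 counts time as the follow-up for the particular event.

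**The concern.** The study size was chosen partly to give informative confidence intervals for SAE incidence rates. For non-malignancy SAEs, the person-time behind such a rate ends at the earliest of study exit, 5 years, and the last DMF dose plus the post-dose window. Two processes shorten it: withdrawal from the study and discontinuation of DMF. Section 9.5 budgets for the first and names only the first as a reason to recruit more.

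If patients stop DMF early but stay in the study, total follow-up can meet its target while the person-years for serious infections, hepatic events and renal events fall well below the 17,000 behind Table 5. The stated condition for enlarging enrolment would not be met, and Table 5 would promise narrower intervals than the data can give.

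**Working it through.** **Inputs from the protocol.** N = 5000 treated patients and 16,000 to 18,000 person-years, 17,000 in Table 5 (Section 9.5); at most 5 years per patient (Section 9.2.1.2); SAE window of 30 days after the last dose (Section 9.2.1.3.1) or 6 months (Annex 2).

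**Inputs assumed.** The protocol states no withdrawal rate and no DMF discontinuation rate. I take constant, independent hazards, *h* for study withdrawal and *d* for stopping DMF, with *d* = 0.10, 0.20 or 0.30 per year and no restarts. As annual probabilities, 1 − exp(−*d*), these are 9.5, 18.1 and 25.9%.

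**Step 1: the plan's own figures.** The person-year forecast cannot be derived without a withdrawal rate, but it can be inverted. Solving 5000 × (1 − exp(−5*h*))/*h* = 17,000 gives *h* = 0.1656 per year, that is 1 − exp(−0.1656) = 15.3% per year. For 16,000 and 18,000 the annual figures are 17.6% and 13.0%. In Table 5, five cases in 17,000 person-years give 29.4 per 100,000 with exact Poisson limits of 9.55 and 68.6 (printed as 9.6 and 68.6).

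**Step 2: SAE-observable time with study follow-up held at 17,000.** With post-dose window *w* in years,

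PY = 5000 × { (1 − exp(−*hw*))/*h* + exp(−*hw*) × (1 − exp(−(*h*+*d*)(5−*w*)))/(*h*+*d*) }.

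For *d* = 0.20 and *w* = 30/365.25 = 0.0821, the first term contributes about 408 person-years and the second about 11,256, in total about 11,660.

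**Step 3: precision.** On the log scale, Poisson interval width varies as 1/√(number of events). At a given true rate, the width relative to plan is therefore √(17,000/PY).

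| DMF stop hazard *d* (assumed) | PY, 30-day window | Share of 17,000 | Interval width vs plan | PY, 6-month window |
|---|---|---|---|---|
| 0.10 | about 13,900 | 82% | 1.10 | about 14,500 |
| 0.20 | about 11,700 | 69% | 1.21 | about 12,600 |
| 0.30 | about 9,900 | 58% | 1.31 | about 11,100 |

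If 10, 20 and 30% are read as annual probabilities rather than hazards, the 30-day figures are about 13,800, 11,200 and 9,100.

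**Step 4: what this does to a Table 5 row.** At *d* = 0.20 with the 30-day window, five cases give 5/11,660 = 42.9 per 100,000 person-years. The exact limits scale by 17,000/11,660 = 1.458: 9.55 × 1.458 = 13.9 and 68.6 × 1.458 = 100.0.

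**The case against.** The strongest reply is that the clause is permissive. It sets no threshold and does not say that withdrawal is the only admissible reason. Section 10.3 provides for amendments. Safety is analysed after 1000 patients have 6 months of follow-up and at least annually after that (Section 9.7.8). DMF start date, duration of use and stop date are collected, and duration is summarised (Section 9.7.4). A shortfall in exposure would thus be visible and could be acted on. This stands, and it limits the point to what the protocol tells the team to watch and what precision it states.

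The term is also undefined and rests partly on rates from DMF clinical trials, so it might include stopping treatment. That cannot be excluded. However, the separate headings in Section 9.2.1.3, and the Section 9.5 sentence that follow-up continues after discontinuation, favour study withdrawal. If both were meant, the text should say so.

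A reader might infer that the clause watches something irrelevant to the primary endpoint. The documents do not support that. Withdrawal ends all SAE observation. In the model above it alone reduces 5000 × 5 = 25,000 possible person-years to 17,000, and for malignancies, which are collected after DMF stops, study retention is the main determinant. A reader might also count AEs leading to discontinuation as lost. They are recorded when DMF is stopped, and a patient who is off the drug and does not restart cannot have another, so nothing of that component is missed.

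Finally, restarts are allowed under Section 9.2.1.3.1 and resume full collection, which would reduce the loss.

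**Conclusion.** The point holds in a limited form. For SAEs other than malignancies, observable time depends on both study withdrawal and DMF discontinuation, while Section 9.5 and Table 5 are built on study follow-up and the enrolment clause names only withdrawal.

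With 17,000 study person-years, constant DMF stop hazards of 0.10 to 0.30 per year, no restarts and the 30-day window, SAE-observable time is 82 to 58% of the Table 5 figure and log-scale intervals are 10 to 31% wider. The 6-month window gives a smaller shortfall. These sizes rest on assumed discontinuation rates, because the protocol gives none.

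It would be wrong to infer that the safety results would be biased or that a planned test would fail. Section 9.7 plans no formal hypothesis testing, and Section 9.7.3 adjusts each rate for its own follow-up, so wider intervals would reflect the smaller exposure. The incidence proportion also keeps its denominator of 5000, although fewer events would be seen. Nor do the documents show that a shortfall would come to light only after enrolment had closed. This is an inexpensive improvement of modest importance.

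**What to change.** In Section 9.5:

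- State the expected SAE-observable person-years (first DMF dose to last dose plus the post-dose window) beside the 16,000 to 18,000 figure, with the DMF discontinuation rate assumed.
- Use that figure for the non-malignancy rates in Table 5, and keep total follow-up for malignancies.
- Reword the discretionary clause along these lines: enrolment may be increased if study withdrawal is substantially greater than expected, or if projected SAE-observable person-years fall substantially below expectation.
- Review both quantities at the planned interim analyses while enrolment is open.

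Reconcile the 30-day and 6-month statements of the SAE window first, since the expected figure depends on it.

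The cost is protocol wording plus one exposure summary at each interim analysis, from dates already collected. The clause remains discretionary, so nothing forces a larger study. The downsides are that it may be invoked more often and that the stated precision for non-malignancy SAE rates becomes less favourable. Five-year exposure can only be projected during enrolment, so the revised clause would still rest on a forecast.

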9.6. Data Management

Data collection will be performed using electronic or paper Case Report Forms (CRFs). Data will be entered into a central database managed by a CRO.

9.7. Data Analysis

Statistical analyses will generally be descriptive and exploratory in nature. No formal statistical hypothesis testing is planned.

9.7.1. Analysis Population

Statistical analyses will be based on all patients who enroll in the study (defined as having an available date of informed consent) and take at least 1 dose of DMF.

9.7.2. Demography and Baseline Disease Characteristics

Demographic and baseline disease characteristics will be summarized by descriptive summary statistics for continuous variables and frequency distribution for categorical variables.

Analyses of SAEs, AEs leading to treatment discontinuation, and clinical laboratory parameters may also be undertaken for patient subgroups defined by appropriate demographic and/or baseline prognostic factors, and/or concomitant medication exposure (e.g., concomitant MS therapies and potentially nephrotoxic medications). Analyses may also be stratified by treatment duration or study duration epochs.

9.7.4. DMF Prescription and Utilization

Duration of DMF use and prescribed dosing frequency will be summarized both descriptively and categorically, as appropriate. Primary reasons for discontinuation of DMF will be tabulated.

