9.1.2. Secondary Endpoints

Secondary endpoints will address non-safety related study objectives, as follows:

- DMF prescription and utilization patterns will be evaluated by assessment of prescribed dosing frequency, duration of DMF use, and primary reason for discontinuation of DMF (see Section 9.7.4).
- Effectiveness of DMF on MS disease activity and disability progression will be evaluated by assessment of relapse-related endpoints (e.g., annualized

CONFIDENTIAL

The information contained herein may not be used, disclosed, or published without the written consent of Biogen Idec MA Inc.

relapse rate, time to first relapse, proportion of patients with relapse, and distribution of the number of relapses) and by assessment of EDSS-based disability progression-related endpoints (e.g., proportion of patients with progression and time to first progression), respectively (see Section 9.7.5).

- Changes in health-related quality of life measures will be evaluated over time. Healthcare resource consumption will be evaluated by assessment of endpoints such as number of hospitalizations, emergency room visits, and neurologist visits. Work productivity will be evaluated by assessment of ability to work and time needed away from work due to MS (see Section 9.7.6).

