9.2.1.3.3. Premature Withdrawal From the Study

Patients may withdraw consent to participate in the study at any time. If withdrawal occurs during a routine clinical visit, the Prescribing Physician will collect information one last time following the standard protocol as described in Section 9.3.2, if permitted by the patient. If a patient withdraws from the study outside of the physician's office, information will be collected one last time by telephone according to the standard protocol, with the exception of laboratory data and EDSS score, if permitted by the patient.

For patients who discontinue DMF and continue to participate in the study but subsequently withdraw, similar information will be collected one last time at the time of withdrawal, but SAE data collection will be limited as described in Section 9.2.1.3.1.

For patients who do not initiate treatment with DMF and continue to participate in the study but subsequently withdraw, similar information will be collected one last time at the time of withdrawal except SAE and pregnancy data as described in Section 9.2.1.3.2.

CONFIDENTIAL

[figure not shown]
The information contained herein may not be used, disclosed, or published without the written consent of Biogen Idec MA Inc.

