9.2.1.3.4. Lost to Follow-Up

If a patient has not been in contact with the Prescribing Physician for 12 months following his or her last routine visit, the site will contact the patient by telephone to assess the patient's interest in continuing study participation. If the site is unable to make contact with the patient, a follow-up attempt must be made. A site may consider a patient lost to follow-up after 3 failed documented contact attempts, one of which must be a certified letter. If a patient's status is determined to be lost to follow-up, this must be recorded on the End of Study CRF. If the physician ascertains a patient has died, the death should be recorded and reported as described in Section 11.2.4.1.

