9.7.5. Effectiveness

The effectiveness of DMF on MS disease activity and disability progression will be based on assessment of relapse-related endpoints and EDSS-based progression-related endpoints, respectively. Effectiveness evaluations will include comparisons to external databases.

MS disease activity will be assessed by evaluating the frequency of relapses over time. These analyses may include the following parameters:

- annualized relapse rate
- time to first relapse
- proportion of patients with relapse
- distribution of the total number of relapses

Disability progression will be assessed by evaluating EDSS evolution over time. These analyses may include the following parameters:

- proportion of patients with progression (defined as at least a 1.0 point increase from a baseline EDSS ≥ 1.0 or at least a 1.5 point increase from a baseline EDSS = 0)
- time to first progression
- proportion of patients with sustained progression for at least 6 months
- time to sustained progression for at least 6 months
- proportion of patients with post-baseline EDSS values greater than certain thresholds (e.g., ≥ 4.0 , >6.5) at any time and sustained for at least 6 months

CONFIDENTIAL

The information contained herein may not be used, disclosed, or published without the written consent of Biogen Idec MA Inc.

[figure not shown]
- proportion of patients whose disability status worsened, stabilized, or improved over time, including an analysis based on values sustained for at least 6 months. Improvement may be defined as a decrease of at least 1.0 point from baseline, a stable condition as a change of ≤ 0.5 point from baseline, and worsening as an increase of at least 1.0 point from baseline.

Annualized relapse rate will be analyzed using a negative binomial model, adjusted for appropriate prognostic factors, and time-to-event endpoints will be analyzed using Kaplan-Meier estimates. Analyses of relapse related and progression related endpoints may also be undertaken for patient subgroups defined by appropriate demographic and/or baseline prognostic factors (e.g., EDSS score).

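### Section 9.7.4 summarises duration of DMF use with no allowance for patients who leave the study still on DMF; read as time on drug, the result is biased downward by an amount the protocol does not identify

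*Protocol*

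**What the plan says.** Utilisation appears in the study title and is the first secondary objective (Protocol 8.2). Section 9.1.2 says it will be "evaluated by assessment of prescribed dosing frequency, duration of DMF use, and primary reason for discontinuation of DMF". Section 9.7.4 gives the whole analysis of duration: "Duration of DMF use and prescribed dosing frequency will be summarized both descriptively and categorically, as appropriate". It has no rule for a patient who is still taking DMF when observation ends.

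Observation can end in several ways:
- Section 9.2.1.2: "Patient participation in the study will be for up to 5 years from enrollment".
- Section 9.2.1.3.3: "Patients may withdraw consent to participate in the study at any time".
- Section 9.2.1.3.4: "A site may consider a patient lost to follow-up after 3 failed documented contact attempts".
- Section 9.2.1.3.5 covers transfer to another physician. The sponsor will look for another study site or may add the new one, but continuation is not assured.

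Section 9.2.1.3.1 makes staying in the study after stopping DMF optional and allows DMF to be restarted at any time within the 5 years.

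Section 9.5 expects that, on the basis of withdrawal rates, "approximately 16,000 to 18,000 person-years of follow-up will accrue" from 5000 treated patients.

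For other outcomes a censoring-aware method is named. Section 9.7.5 (Effectiveness) says "time-to-event endpoints will be analyzed using Kaplan-Meier estimates", and the Data Analysis row of the abstract repeats this in the same sentence as the annualised relapse rate. Nowhere is duration of DMF use called a time-to-event endpoint.

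**The concern.** A patient's time on DMF is fully known only if DMF is stopped under observation. For a patient who leaves the study on drug, the recorded duration is a lower limit. A mean, median or category count that takes it at face value mixes time on the drug with time in the study, and the error runs one way. Shares in the longer-use categories come out too low and the median too short.

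Patients who reach 5 years still on DMF are a different case. They truncate the mean and the upper tail but do not distort proportions or quantiles within 5 years. That distortion comes only from early exit while on drug.

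Interim reports are more exposed. Section 9.7.8 lets other objectives follow the safety schedule, which starts once 1000 patients have 6 months of follow-up. At that stage most patients' recorded duration is set largely by when they enrolled.

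At stake is the reading of a secondary endpoint on utilisation, not the primary safety result.

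**Working it through.** The protocol states no figure for duration of use, so there is none to reproduce. The check asks how far an unadjusted summary could fall below the true one, given the person-years in section 9.5.

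**Inputs from the protocol.** 5000 treated patients, follow-up capped at 5 years, and 16,000 to 18,000 person-years expected (17,000 is used for Table 5). The maximum would be 5000 × 5 = 25,000, and mean follow-up is 3.2 to 3.6 years.

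**Assumptions, not in the protocol.** Constant hazards, and a DMF stopping rate m. The main case is m = 0.15 per year; other values are tried below.

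**Step 1: study-exit rate w.** Solve (1 − e^(−5w))/w = mean follow-up.
- 16,000: w = 0.194; 38% complete 5 years.
- 17,000: w = 0.166; 44% complete.
- 18,000: w = 0.139; 50% complete.

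So 50% to 62% leave the study before year 5. This counts all exits, on or off DMF.

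**Step 2: true time on drug, m = 0.15.** Median ln 2/0.15 = 4.62 years. On DMF at 2 years: e^(−0.30) = 74%. At 5 years: e^(−0.75) = 47%. Mean within 5 years: (1 − e^(−0.75))/0.15 = 3.52 years.

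**Step 3: unadjusted summary at 17,000 person-years, two scenarios.**

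*A. Exit is independent of stopping.* Recorded time on drug ends at rate m + w = 0.316. Share leaving on DMF: (0.166/0.316) × (1 − e^(−5 × 0.316)) = 42%.

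*B. Stoppers leave the study at once.* All exits together run at 0.166, so on-drug exit is 0.166 − 0.15 = 0.016, and recorded time on drug ends at rate 0.166. Share leaving on DMF: (0.016/0.166) × (1 − e^(−5 × 0.166)) = about 5%.

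| m = 0.15, 17,000 person-years | True | A | B |
|---|---|---|---|
| Median (years) | 4.6 | ln 2/0.316 = 2.2 | ln 2/0.166 = 4.2 |
| On DMF ≥ 2 years | 74% | e^(−0.63) = 53% | e^(−0.33) = 72% |
| On DMF at 5 years | 47% | 21% | 44% |
| Mean within 5 years | 3.5 | 2.5 | 3.4 |

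**Step 4: other values.**
- 16,000 person-years, m = 0.15: A gives a median of ln 2/0.344 = 2.0 years; B gives ln 2/0.194 = 3.6.
- 18,000 person-years, m = 0.15: A gives ln 2/0.289 = 2.4 years. For B, m already exceeds w = 0.139, so the person-years are compatible with no on-drug exit and no bias within 5 years.
- 17,000 person-years, 10% stopping per year (m = 0.105): true median 6.6 years, beyond follow-up; A gives 2.6, B gives 4.2. Use for at least 2 years: 81% true, 58% in A, 72% in B.
- 17,000 person-years, 30% stopping per year (m = 0.357): true median 1.9 years; A gives 1.3. Use for at least 2 years: 49% true, 35% in A. Here m exceeds w, so no on-drug exit, and hence no bias, is also possible.

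Scenario A is not a limit on the bias. If stoppers were less likely to leave than patients still on drug, on-drug exit would have to exceed 0.166 to give the same person-years.

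**The case against.** Four points on the other side have weight.

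**Estimators are SAP matter.** Annex 2 defers detailed analysis to an SAP that is not shown. The wording in 9.7.4 leaves room for discretion, and a Kaplan-Meier curve is itself descriptive. This stands in part: the protocol does not forbid the better analysis. But it names a method for this endpoint, a different one from that for time-to-event endpoints, and an SAP could follow 9.7.4 to the letter and report the biased figure.

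**Observed exposure is a legitimate quantity.** The protocol never uses the word persistence, and exposure up to last contact is known. This stands. The table is sound if labelled as such; the bias arises only when it is read as time on drug, which an endpoint called duration of use invites.

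**The person-years do not show heavy censoring on drug.** A reader might infer from 16,000 to 18,000 out of 25,000 that many patients leave while on DMF and that apparent use is roughly halved. The documents do not support that. The person-years measure exit from the study, and follow-up after stopping is optional, so exits may cluster among stoppers. Scenario B then leaves a small shortfall.

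**Completers and transfers.** A reader might also add those on DMF at 5 years to the biased share, or count every transfer as lost. Completers do not bias shares within 5 years, and section 9.2.1.3.5 tries to keep transferring patients in the study.

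Nor is Kaplan-Meier confined to section 9.7.5. The abstract states it too, though next to relapse rate and without mention of duration of use.

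**Conclusion.** The point holds as a defect of method whose size is unknown. Section 9.7.4 names only a descriptive and categorical summary for a secondary endpoint that is right-censored for anyone leaving the study on DMF. Read as time on drug, the result errs only downward, and more at interim reports.

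On 17,000 person-years and an assumed stopping rate of 0.15 per year, the median would be shown as 2.2 to 4.2 years against 4.6, and use for at least 2 years as 53% to 72% against 74%. The ends of the range correspond to exit independent of stopping and to stoppers leaving at once. The figures rest on constant hazards and an assumed stopping rate. At higher stopping rates or 18,000 person-years, no bias within 5 years is also compatible with the protocol. A claim that time on DMF will be grossly understated goes beyond the documents; a claim that the named method suits the endpoint does too. The change is worth making because it is cheap and removes the dependence on which scenario is true, provided that censoring is non-informative.

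**What to change.** In section 9.7.4:

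1. Add a Kaplan-Meier estimate of time from first dose to first DMF discontinuation. Censor patients still on DMF at last contact or end of follow-up.
2. State a rule for gaps and restarts, since section 9.2.1.3.1 allows DMF to be resumed.
3. Report the proportion still on DMF at years 1 to 5 with 95% CIs, at the final analysis and, as far as follow-up allows, at any interim report that covers utilisation.
4. Keep the descriptive and categorical table, labelled 'observed DMF exposure during the study'.
5. State that censoring is assumed non-informative. A patient who stops DMF and is lost before the stop is recorded would be counted as still on drug, and the estimate would then be too long.

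Cost: a few sentences and one extra analysis. No new data are needed: the start date (9.3.1), duration of use (9.3.2) and discontinuation date (Table 7, Chart 2) are already collected.
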